#### 4.3.2.1.1. Sensitivity Analysis

The following sensitivity analyses are planned for supportive inference using the ITT population:

- 1) The status of clinical recovery at Day 15 analysis will be repeated using the single imputation method of Last Observation Carried Forward (LOCF) rather than the multiple imputation approach described in [Section 3.10.1](#)
- 2) Clinical status will be dichotomized over time, where subjects will be classified as either improved (Yes) or declined/no change (No) based on the 6-point scale result from the baseline visit. Subjects who are discharged or deceased over time will not contribute to subsequent timepoints. The treatment effect will be analyzed via generalized linear mixed models using SAS PROC GLIMMIX, with improvement in clinical status (yes/no) as the dependent variable, and treatment group, disease severity, and visit as independent variables. Least-squares means of the treatment group effect on the logit scale (difference on the log odds) will be utilized for analysis, where the odds ratio and corresponding 90% CI will be provided

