### 1.2.2. Randomization Methodology

Subjects will be evaluated for eligibility during Day 1, prior enrollment in the study or starting treatment. The randomization procedure will be performed centrally using the electronic data capture (EDC) system, IBM Clinical Development.

Approximately 50 subjects are planned to be randomized at a 1:1 ratio to receive either favipiravir + SOC or SOC alone. Randomization will be stratified by site and severity of illness at enrollment. Severity of illness at enrollment will be graded (i.e., critical disease, severe disease, or mild/moderate disease) as follows:

- Critical disease:
  - Requires supplemental oxygen delivered by non-rebreather mask or high-flow cannula, OR
  - Requires use of invasive or non-invasive ventilation, OR
  - Requires treatment in an intensive care unit, use of vasopressors, extracorporeal life support (i.e., extracorporeal membrane oxygenation [ECMO]).
- Severe disease:
  - Evidence of pneumonia on chest x-ray or computed tomography (CT) scan, or chest auscultation (rales, crackles), OR
  - Peripheral capillary oxygen saturation ( $SpO_2$ )  $\leq$  93% on room air OR partial pressure of oxygen ( $PaO_2$ )/fraction of inspired oxygen ( $FiO_2$ )  $<$  300 mmHg, OR
  - Requires supplemental oxygen by nasal canula, simple face mask, or other similar oxygen delivery device.
- Mild/moderate disease:  $SpO_2 > 94\%$  and respiratory rate  $\leq 24$  breaths/min without supplemental oxygen

The randomization will target balance within stratum. This does not guarantee balance overall; however, utilizing a block size of 2, as well as with sufficient sample size within strata, balance will be approximately maintained while pooling across sites.

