## 1.2.6. Efficacy, Pharmacokinetic, and Safety Parameters

### 1.2.6.1. Efficacy Parameters

Efficacy will be measured through the following parameters:

For Primary Endpoint:

- PCR in the nasopharyngeal and oropharyngeal samples taken on Days 1, 3, 8, 11, 15 and 29. Swabs will also be obtained on day of discharge from hospital if discharge occurs before Day 15.

For Secondary Endpoint:

- Clinical improvement of hospitalized subjects with COVID-19 receiving either favipiravir + SOC or SOC alone as defined by the following study-specific 6-point ordinal scale assessed daily while hospitalized and at each outpatient visit until Day 60..
  1. Not hospitalized
  2. Hospitalized, not requiring supplemental oxygen
  3. Hospitalized, requiring supplemental oxygen
  4. Hospitalized, on non-invasive ventilation or high flow oxygen devices
  5. Hospitalized, on invasive mechanical ventilation or ECMO
  6. Death
- NEWS2 assessed daily while hospitalized and at each outpatient visit until Day 60.
- Vital signs (BP, HR, RR, BT, SpO2) measured daily while hospitalized and at each outpatient visit until Day 60.
- Patient status assessed daily while hospitalized and at each outpatient visit until Day 60 via Study-specific Symptom Status and ECOG Performance Status questionnaires
- Period of each respiratory assistance (if applicable).
- Period of hospitalization.
- Period of intensive care unit (if applicable).
- Date and cause of death (if applicable).
- TCID50 in nasopharyngeal and oropharyngeal swabs on Days 1, 3, 8, 11, 15 and 29. Swabs will also be obtained on day of discharge from hospital if discharge occurs before Day 15.

Note: Since TCID50 for SARS-CoV-2 is not yet proven to be sensitive for detection of the virus and is still under development for that purpose, analyses using TCID50 will not be conducted if TCID50 for SARS-CoV-2 is not detectable enough.
- Blood for determination of antibodies to SARS-CoV-2 obtained on Days 1, 15 and 29.

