## **2. SUBJECT POPULATION**

### **2.1. Population Definitions**

The following subject populations will be evaluated and used for presentation and analysis of the data:

- Intent-to-treat (ITT) population – All subjects randomized to treatment. Subjects in the ITT population will be analyzed based on the treatment to which they were randomized, irrespective of what treatment they actually received. This population was selected for the analysis of the primary and secondary endpoints in order to maintain the benefits of randomization and avoid the potential bias associated with the non-random loss of the participant.
- Safety population – All ITT subjects who received either favipiravir + SOC or SOC alone. Subjects in the safety population will be analyzed based on the actual treatment they received, irrespective of the treatment to which they were randomized. It is anticipated that the safety population will be the same as the ITT population.
- Modified intent-to-treat (mITT) – All subjects of the ITT population that have a post-baseline assessment of viral shedding and at least one PCR positive result for SARS-CoV-2 in any protocol-required swab samples. Note that results recorded as less than the lower limit of quantification (LLOQ) are considered to be negative. Subjects in the mITT population will be analyzed based on the treatment to which they were randomized, irrespective of what treatment they actually received.
- Per protocol (PP) population – All mITT subjects who adhere to relevant study procedures (i.e. have no major protocol deviation that would be expected to affect efficacy assessments) and have an outcome assessment.
- PK population (PK) – All subjects in the safety population that have at least one result that can be used in the PK summaries.

The ITT population is the primary population for the analysis of efficacy parameters; the mITT and PP populations will be used for supportive inferences concerning efficacy. The PK population is the primary population for the analysis of PK parameters. The Safety population is the primary population for the analysis of safety endpoints.

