## 3.11. Visit Windows

It is expected that all visits should occur according to the protocol schedule. However, analysis visits will be derived based on study day for all by-visit summaries and analyses. Analysis visit designations are detailed in [Table 3-1](#).

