**Table 3-1 Post-Baseline Analysis Visit Designations**

| Analysis Visit | Analysis Visit Range |
|-----------------------|-----------------------------|
| Day 1                 | Day 1                       |
| Day 2                 | Day 2                       |
| Day 3                 | Days 3-5                    |
| Day 8                 | Days 6-9                    |
| Day 11                | Days 10-12                  |
| Day 15                | Days 13-17                  |
| Day 21                | Days 18-24                  |
| Day 29                | Days 25-33                  |
| Day 45                | Days 34-52                  |
| Day 60                | Days 53-70                  |

In the event there are multiple assessments within a given analysis range, the value closest to the target day (understood to be the day identified in the analysis visit) will be chosen. If more than one measurement are the same distance from the target day, the earlier visit will be chosen.

In data listings, the relative day of all dates will be presented.

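### The supportive improved/not-improved model (SAP 4.3.2.1.1, item 2) drops subjects after discharge or death, so it does not test the same question as the Day 15 model it supports (minor)

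*SAP*

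**What the plan says.** SAP 4.3.2.1.1 lists two sensitivity analyses of the ordinal scale, both in the ITT population. Item 2 classes each subject over time as improved (Yes) or as declined/unchanged (No) relative to baseline. It then adds the rule "Subjects who are discharged or deceased over time will not contribute to subsequent timepoints". On the model it says: "The treatment effect will be analyzed via generalized linear mixed models using SAS PROC GLIMMIX, with improvement in clinical status" as the outcome, and "treatment group, disease severity, and visit as independent variables". It names no random effect and has no treatment-by-visit term, so it yields one pooled odds ratio.

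Four other places bear on this:

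- SAP 1.2.6.1 makes level 1 not hospitalized and level 6 death, with the "6-point ordinal scale assessed daily while hospitalized and at each outpatient visit until Day 60".
- SAP 4.3.2.1 (main Day 15 model) sets a missing Day 15 status to level 1 after an earlier discharge and to level 6 after an earlier death.
- SAP 2.1 says ITT was chosen to "maintain the benefits of randomization and avoid the potential bias associated with the non-random loss of the participant".
- SAP 3.11 says "analysis visits will be derived based on study day for all by-visit summaries and analyses". Under Table 3-1, "In the event there are multiple assessments within a given analysis range, the value closest to the target day" is the one used.

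**The concern.** Subjects enter hospitalized and not on a ventilator (Protocol 5.1 and 5.2), so baseline is taken as level 2, 3 or 4. Discharge is then always an improvement and death always a decline. Both are known outcomes, yet item 2 treats the subject as absent from the next timepoint on. What remains at later visits is a group selected after randomization by slow recovery and survival. If treatment changes how fast people leave hospital or die, the two arms are selected differently.

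At stake is the use of item 2 as support for the Day 15 result. A sensitivity analysis should vary an assumption and keep the question. This one changes the question, and it can mute a mortality difference or make faster discharge look like a lack of benefit. That matters because a secondary objective (SAP 1.1.2) asks whether the scale can serve as the primary clinical endpoint of a later blinded study.

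**Working it through.** **No plan figure to reproduce.** Neither document gives a discharge rate, a death rate or an expected odds ratio for this model. The planned 25 per arm (SAP 3.1) is used below only to judge sampling error.

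**1. How often one outcome counts.** Take a death on Day 4. Carried forward, it is No at Days 8, 11 and 15 (3 visits), and also at Days 21, 29, 45 and 60 (7 visits in all). Under the drop rule it is No once if credited at the next visit. Under a literal reading of the windows it is not counted.

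**2. The windows, read literally.** Assume the event-day record is already level 1 or 6. A subject in hospital on the target day has a score for that day, and that score is the closest. An event later in the same window loses to it, and the next visit is already a subsequent timepoint.

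| Visit | Window | Event days never scored |
|---|---|---|
| Day 2 | 2 | none |
| Day 3 | 3-5 | 4, 5 |
| Day 8 | 6-9 | 9 |
| Day 11 | 10-12 | 12 |
| Day 15 | 13-17 | 16, 17 |
| Day 21 | 18-24 | 22, 23, 24 |

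To Day 15: 2 + 1 + 1 = 4 of the 14 days 2-15. To Day 29: 4 + 2 + 3 = 9 of the 28 days 2-29. If the discharge-day record still shows inpatient status and level 1 appears only at a return visit, 19 of 28 discharge days go unscored. If events are credited at the next visit, none do, but all visits after that one are still lost.

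Example: the mild/moderate stratum ends with "breaths/min without supplemental oxygen", so a hospitalized subject there starts at level 2 and can improve only by discharge. Discharged on Day 4 or 5, this subject is No at Days 2 and 3 and never scored again, as if never improved.

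**3. Effect on the odds ratio (all rates assumed).** Each subject starts unimproved on Day 1. Each day an unimproved subject improves or dies with fixed probabilities, and an improved inpatient is discharged with a fixed probability. Base daily rates, SOC v favipiravir: improvement 10% v 18%, discharge once improved 18% v 32%, death while unimproved 1.2% in both. All paths are enumerated. The fitted model is logit P(Yes) = visit effect + b x treatment, at Days 2, 3, 8, 11 and 15, and the odds ratio is exp(b). Severity is left out and there is no random effect.

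| Case | Next visit | Literal windows | Carried forward |
|---|---|---|---|
| Base | 2.21 | 2.06 | 2.52 |
| Only discharge differs (18% v 32%) | 0.88 | 0.83 | 1.00 |
| Only death differs (1.2% v 3.0%) | 1.01 | 1.03 | 0.87 |

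On the base rates the literal windows never score 31% (SOC) and 36% (favipiravir) of discharges by Day 15, and 31% of deaths.

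**4. Against sampling error.** Distance from carried forward on the log scale, next visit and literal windows:

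- Base: 0.92 - 0.79 = 0.13 and 0.92 - 0.72 = 0.20.
- Only discharge differs: 0.13 and 0.19.
- Only death differs: 0.01 + 0.14 = 0.15 and 0.03 + 0.14 = 0.17.

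Simulated at 25 per arm, the log odds ratio has an SD of about 0.54 to 0.56 in the base case and 0.53 in the death case. In those two cases the shifts are roughly a quarter to a little over a third of one SD.

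**5. With a subject random intercept (SD 2, assumed).** Same column order: base 4.54 / 4.23 / 4.80, discharge 0.94 / 0.90 / 1.00, death 0.98 / 1.03 / 0.78. In the base case the log odds ratio is ln 4.54 / ln 4.80 = 96% and ln 4.23 / ln 4.80 = 92% of carried forward.

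**The case against.** The strongest reply is that item 2 is a separate, labelled sensitivity analysis whose different handling is written down. Status while in hospital is a legitimate quantity, and treating carried forward as the benchmark presumes a composite with death. ITT governs who is analysed and in which arm, and every subject enters until the event. The outcomes are covered elsewhere: the Day 15 model, the longitudinal ordinal model with its visit-by-treatment term, time to clinical recovery, and the mortality analysis in SAP 4.3.2.7. P-values other than the primary are descriptive (SAP 3.2). The effect is small beside the noise at 25 per arm, and in the base case smaller still with a random intercept.

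Most of this stands and sets the severity. It does not remove the point: the SAP does not say that item 2 targets status while hospitalized, and offers it as support for a model that handles discharge and death in the opposite way.

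Two stronger readings are tempting. A reader might infer that some discharges and deaths are certainly never scored. That needs the literal window reading with the event-day record already at level 1 or 6. Crediting the event at the next visit is an equally natural reading, and the SAP does not choose. A reader might also infer that 4.3.2.1 and item 2 contradict each other, or that item 2 breaches ITT. The Day 15 rules cover a missing Day 15 status in another model, so this is a difference in the question asked and not a contradiction.

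**Conclusion.** The point holds and is minor. As written, item 2 removes subjects once they reach either end of the scale it dichotomizes, so it does not check the Day 15 result on the same question. That follows from the text and needs no assumed rate. Whether some events are never scored depends on how the windows are read.

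The size rests on assumed rates, on a model without severity, and on whether a random effect is fitted. On those assumptions the pooled odds ratio moves by less than its sampling error. The documents do not support the inference that item 2 is biased in a known direction, or that the trial's main conclusions are at risk. The primary endpoint, main Day 15 model, longitudinal ordinal model, mortality analysis and sample size do not use this rule.

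**What to change.** In SAP 4.3.2.1.1 item 2, replace the drop sentence with wording to this effect: discharged subjects stay in the analysis as improved (Yes) at every later visit, using the recorded outpatient score or readmission status where there is one; deceased subjects stay in as not improved (No) at every later visit; a discharge or death after the target day of a Table 3-1 window is scored from the next visit.

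The cost is about two sentences. Hospitalization period and date of death are already collected (SAP 1.2.6.1), and no other analysis changes. Two downsides should be stated:

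- A decline after discharge may be missed if no visit takes place.
- Carried-forward rows are highly correlated within subject (the Day 4 death becomes seven No rows to Day 60), so a subject random-effect variance may be poorly estimated. The SAP should say how this correlation is handled, for example with a marginal model and robust standard errors.

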#### 4.3.2.2. Time to Clinical Recovery

The time to clinical recovery (TTCR) assessed up to 29 days will be analyzed in a similar manner as the primary efficacy endpoint. TTCR is defined as the time (in days) from initiation of study treatment (favipiravir + SOC or SOC alone) until normalization of fever, respiratory rate, oxygen saturation, and alleviation of cough, sustained for at least 72 hours; or hospital discharge. The normalization and alleviation criteria are presented in [Table 4-1](#).

**Table 4-1 Normalization and Alleviation Criteria**

| Parameter         | Criteria   |
|-------------------|--|
| Fever             | $\leq 37.2$ °C   |
| Respiratory Rate  | $\leq 24$ breaths/minute on room air   |
| Oxygen Saturation | SpO 2 > 94% on room air   |
| Cough             | Mild or absent on a subject-reported scale of severe, moderate, mild, absent |

Subjects with no evidence of clinical recovery will be censored at last assessment of the parameter that is not be recovered. The censoring rules as provided in Section 4.3.1 will also be employed. In addition, if a subject achieves TTCR and then discontinues from the study during the 72 hour confirmation period, it will be censored at the discontinuation. If a subject achieves TTCR and then discharge, it will be confirmed as recovered at the time of achieving TTCR.

The difference between treatment groups will be analyzed using a log-rank test at the two-sided alpha level of 0.10, where the p-value will be presented for descriptive purposes (and using a stratified log-rank test by disease severity as a sensitivity analysis).

Analyses of TTCR will be done on the ITT population. Only patients with at least one abnormal result (among the four symptoms listed in Table 4-1) at baseline (or within 72 hours post baseline) will be included in the analysis.

Kaplan-Meier curves will be provided for the overall ITT population. By-subject data listings will also be provided.

In addition, the analysis will be performed with stratification by disease severity.

The analysis will also be repeated by the dexamethasone usage subgroup, where patients will be categorized as having received dexamethasone if they received it at any time prior to the last assessments of normalization and alleviation criteria.

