### 3.10. Missing, Unused, and Spurious Data

#### 3.10.1. Efficacy Data

Should missing data occur for time-to-event endpoints, such subjects will be included in the log-rank analysis as censored observations as specified in Section 4.3.1.

Missing clinical outcome data for secondary efficacy endpoints (other than time-to-event) will be handled by a multiple imputation model that contains the following variables: baseline and post-baseline parameter values, and disease severity, stratified by treatment group. Imputation of missing data will be conducted under a working assumption of missing at random (MAR), meaning that the propensity for a data point to be missing is not related to the missing data, but it is related to some of the observed data.

The imputations will be performed for post-baseline visits. The Fully Conditional Specification (FCS) method will be used, given its natural handling of both ordinal and nominal variables (Liu & De 2015). Predicted Mean Matching (PMM) (using a linear prediction model to obtain predicted values and  $k=5$  for randomly drawing from  $k^{\text{th}}$  nearest observed values to the predicted value) will be implemented under FCS (Schenker & Taylor 1996). One hundred (100) datasets will be imputed in order to estimate the treatment effect, where the median value across the imputed datasets will be used for subjects with missing endpoints.

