### **4.3. Efficacy Evaluation**

#### **4.3.1. Analysis of the Primary Efficacy Endpoint**

The primary endpoint of time to viral clearance will be analyzed with the log-rank test for treatment difference based on a two-sided alpha-level of 0.10 and summarized using Kaplan-Meier methodology. The time to viral clearance (in days) is defined as the time of Negative or Lower Limit of Quantification (LLOQ) results (without any quantitative results after that) as measured by PCR for SARS-CoV-2 via scheduled nasopharyngeal and oropharyngeal swab samples minus the date of first dose + 1.

Subjects who have no evidence of viral clearance will be censored at the time of the last PCR measurement with the following conditions:

- Patients whose symptoms worsen (defined as an increase of  $\geq 1$  point on the 6-point Ordinal Scale from baseline) on the day of the last PCR measurement, or who die will be censored at Day 29,
- Patients who are lost to follow-up will be censored on the day of the last PCR measurement.

The median time to viral clearance will be estimated based on the Kaplan-Meier estimator; additional summary statistics will be presented, including the 25th and 75th percentiles, 90% CIs (the log-log transformation) on the median and other percentiles and proportion of censored subjects. Viral clearance rates at Days 3, 8, 11, 15, and 29 will also be presented.

The analysis of the primary efficacy endpoint will be done using the ITT population.

The primary analysis will be supplemented with a sensitivity analysis, using a stratified log-rank test, where the treatment difference based on a two-sided alpha-level of 0.10 will be summarized and stratified by disease severity.

The analysis will also be repeated by the dexamethasone usage subgroup, where patients will be categorized as having received dexamethasone if they received it at any time prior to the last viral clearance assessment.

Kaplan-Meier curves will be provided for the overall ITT population. By-subject data listings of viral clearance data will also be provided.

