#### 4.3.2.4. Analysis of the National Early Warning Score

The time to aggregate NEWS2 score of  $\leq 2$  (sustained for at least 72 hours) or hospital discharge will be analyzed up to Day 29 in a similar manner as the time to TTCR described in [Section 4.3.2.2](#). Only patients with a score  $>2$  at baseline or within 72 hours post baseline will contribute to the analysis. Subjects will be censored at last assessment of the parameter if there are no events of  $\leq 2$  aggregate scores. The censoring rules as provided in Section 4.3.1 will also be employed. In addition, if a subject achieves the event and then discontinues from the study

during the 72-hour confirmation period, it will be censored at the discontinuation. If a subject achieves the event and then discharge, it will be confirmed as reach the event at the time of aggregate NEWS2 score of  $\leq 2$ ; Kaplan-Meier curves will be provided for the overall ITT population.

In addition, the analysis will be performed with stratification by disease severity.

Additionally, descriptive statistics of mean changes from baseline in aggregate NEWS2 scores to post-baseline visits will be provided by treatment group. This analysis will be performed using the ITT population. Only patients with at least one-post baseline measurement will be included.

By-subject data listings will be provided.

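### Time to clinical recovery and time to NEWS2 of 2 or below each carry two unranked censoring rules, one of them written for PCR swabs, so the same subject can be given two dates.

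*SAP*

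**What the plan says.** SAP 4.3.2.2 (text under Table 4-1) gives time to clinical recovery (TTCR) its own rule, "Subjects with no evidence of clinical recovery will be censored at last assessment of the parameter that is not be recovered", and follows it with "The censoring rules as provided in Section 4.3.1 will also be employed". SAP 4.3.2.4 does the same for the NEWS2 endpoint: "Subjects will be censored at last assessment of the parameter if there are no events of" a score of 2 or below, and again the 4.3.1 rules apply as well.

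SAP 4.3.1 is written for viral clearance. Its default is "Subjects who have no evidence of viral clearance will be censored at the time of the last PCR measurement with the following conditions". There are two conditions. Subjects whose 6-point scale score is at least 1 point worse than baseline "on the day of the last PCR measurement, or who die will be censored at Day 29". For loss to follow-up: "Patients who are lost to follow-up will be censored on the day of the last PCR measurement".

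SAP 3.10.1 sends every time-to-event endpoint with missing data to the same place: "such subjects will be included in the log-rank analysis as censored observations as specified in Section 4.3.1". SAP 4.3.2.3 applies the TTCR methodology to defervescence, cough and dyspnea, although the subsections for those endpoints restate censoring at the last assessment of the parameter.

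Both 4.3.2.2 and 4.3.2.4 add a further rule for subjects who discontinue within the 72-hour confirmation period, and count hospital discharge as an event.

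**The concern.** A subject who is lost to follow-up unrecovered satisfies both the parameter rule and the 4.3.1 loss rule. A subject who dies unrecovered satisfies both the parameter rule and the 4.3.1 death rule. In each case the rules can give different dates, and the SAP does not say which prevails. Two programmers could follow the text faithfully and produce different Kaplan-Meier curves and p-values.

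The imported wording also does not fit a clinical endpoint. A swab date says nothing about when fever, respiratory rate, SpO2, cough or NEWS2 were last seen abnormal, so dating by it discards observed unrecovered days. The worsening trigger is read on the day of the last swab: worsening after that day is missed, and worsening that has since reversed still counts.

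For deaths the choice matters in substance. Censoring at the last assessment removes the death from the risk set as if recovery had still been possible, which overstates recovery. Dating at Day 29 keeps the subject in the risk set as not recovered. In an open-label trial that choice should not be left until the data are in.

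**Working it through.** The documents give no planning figure for TTCR or NEWS2, so there is none to reproduce. The 25 per arm and two-sided 0.10 below come from SAP 3.1 and 3.2.

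**Schedules.** Vital signs, SpO2, symptoms and NEWS2 are recorded every day in hospital (SAP Table 1-1, note 3). For swabs, SAP 1.2.6.1 has "PCR in the nasopharyngeal and oropharyngeal samples taken on Days 1, 3, 8, 11, 15 and 29", plus the day of discharge if before Day 15. Discharge is itself an event here, so that extra swab does not help a censored subject.

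**Loss in hospital, no Early Termination visit.** Let d be the last clinical day.

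- Parameter rule: date = d.
- 4.3.1 rule: date = last scheduled swab on or before d.
- Gap = d minus that swab day.

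| Last clinical day | Last swab | Gap (days) |
|---|---|---|
| 7 | 3 | 4 |
| 10 | 8 | 2 |
| 14 | 11 | 3 |
| 24 | 15 | 9 |
| 28 | 15 | 13 |

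Over d = 1 to 28 the gaps sum to 11 (Days 1 to 7) + 3 (Days 8 to 10) + 6 (Days 11 to 14) + 91 (Days 15 to 28) = 111, a mean of 111/28 = 4.0 days. The gap is 4 days or more on 11 of the 28 days (Day 7 and Days 19 to 28). It is 0 on a swab day.

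**Death.** Gap = 29 minus the last clinical day. Last assessed Day 10: Day 10 or Day 29, 19 days apart. Last assessed Day 5: 24 days apart.

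**Still in hospital and unrecovered at Day 29, with a swab that day.** Both rules give Day 29.

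**Effect on the log-rank test.** This is an illustration; every rate in it is an assumption, not a figure from the documents. There are 25 subjects per arm, with exponential recovery times of median 9 and 14 days. Death and loss fall uniformly on Days 3 to 28, and a subject is censored only if that day precedes recovery. Worsening and Early Termination swabs are not modelled. The first comparison sets the parameter rule for everyone against 4.3.1 for everyone (2,000 trials per row). The second puts all deaths at Day 29 and changes only the dating of losses (4,000 trials per row).

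| Death / loss | Subjects of 50 with different dates, full rule sets | Conclusion at 0.10 differs, full rule sets | Conclusion differs, PCR date only |
|---|---|---|---|
| 5% / 5% | 1.9 | 5.3% | 0.9% |
| 10% / 5% | 3.0 | 7.8% | 0.9% |
| 15% / 10% | 4.9 | 9.1% | 1.7% |

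With deaths fixed at Day 29, only about 0.8 to 1.7 of 50 subjects change date. Most of the disagreement therefore comes from deaths.

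**The case against.** The strongest reply is that the text can be harmonised. In 4.3.1 the Day 29 and loss rules are conditions attached to a default. In 4.3.2.2 the default (last PCR) is replaced by the last assessment of the parameter, and the conditions carry over. Deaths then go to Day 29, which is also what is recommended here. That is a natural reading, and it makes the death part a matter of writing down the precedence. It does not settle the rest: the loss rule carried over still names the PCR date, and the worsening rule still depends on the last swab day.

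Three stronger readings are tempting, and the documents do not support them.

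- A reader might infer that any withdrawal loses up to 13 days, for instance Day 25 cut back to Day 15. Protocol 7.5 includes swabs at the Early Termination visit, so a withdrawal with that visit has a swab on the day and little or no gap. Withdrawal is also not the same as the loss to follow-up that 4.3.1 names.
- A reader might infer a material overstatement of recovery. With an assumed median of 6 days, 25 per arm and 10% deaths spread over Days 3 to 28, dating deaths at the last assessment gives 93.2% recovered by Day 29, against 87.0% when they are held to Day 29. That arises only if the explicit death rule is set aside. The rates are assumed, and it is a single-arm proportion, not the comparison between arms.
- A reader might lean on TTCR's place in the testing order of Protocol 9.1. SAP 3.2 and Section 5 remove that hierarchy, and 4.3.2.2 presents the p-value as descriptive.

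**Conclusion.** The contradiction is in the text and should be corrected, but it is modest. Two unranked rules govern TTCR and the NEWS2 endpoint. On the planned schedule they differ by 0 to 13 days for an unrecovered inpatient lost without an Early Termination visit, and by 29 minus the last clinical day for a death. Few subjects are exposed, because discharge is an event for both endpoints and Early Termination visits include swabs. The primary test and the sample size are unaffected.

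Under the assumed death and loss rates of 5 to 15%, the choice between the full rule sets changes the conclusion at 0.10 in about 5 to 9% of trials, and the PCR dating alone in about 1 to 2%. The date gaps rest only on the documents' schedules and hold exactly for swabs taken on their scheduled days. The percentages depend on the assumed rates, timing and medians. Whether the conflict reaches defervescence, cough and dyspnea cannot be settled from the text.

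**What to change.** In SAP 4.3.2.2 and 4.3.2.4, replace the bare reference to 4.3.1 with one ranked rule:

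1. Subjects who die without the event are kept event-free to Day 29.
2. The Day 29 rule for worsening of at least 1 point from baseline on the 6-point scale is explicitly retained, but judged at the last clinical assessment, not on the last PCR day.
3. All other subjects without the event are censored at the last assessment of the endpoint's own parameter, up to Day 29. No PCR date is used.

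Simply deleting the reference would not do, because it would drop the worsening rule without saying so. Keep the existing rule for discontinuation within the 72-hour confirmation period and give it a place in the order. In 3.10.1, amend the cross-reference so that the clinical endpoints point to this rule and not to 4.3.1. In 4.3.2.3, state whether the rule also applies to defervescence, cough and dyspnea.

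The cost is a few SAP sentences, with no change to data collection, visits or sample size.
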